9.5.1 Primary Outcome

Our primary mechanism outcome is pre- to post treatment changes in EO function.

9.5.2 Secondary Outcomes

Secondary outcomes are pre-post treatment changes in mindfulness and spinal stiffness (specific mechanisms), and in CPM, pain-related cognition and therapy factors (non-specific mechanisms). Other secondary outcomes refer to pre-post changes in patient reported clinical status. These are pain intensity, negative affect (anger, anxiety, depression), physical function, sleep disturbance and social support assessed via PROMIS item banks.

9.6 Data Analyses

Primary analyses will be conducted on an ITT basis.

Aim 1: To determine the degree to which MT and SMT produce effects in nonspecific mechanisms.

The primary analyses will employ the two-sample t-test to compare mean change in each nonspecific mechanism within a noninferiority test construct to compare mean change in outcome from pre to post treatment between the two treatment arms. An overall, 2-sided, significance level of 0.05 will be used. Linear mixed models will be used as a supplemental analysis, allowing us to utilize all data collected, account for within subject variation, and model changes over time. The fixed effect part of the model will be

$Mechanism_{ij} = \beta_0 + \beta_1 Time_{ij} + \beta_2 Tx_i + \beta_3 (Tx_i * Time_{ij}) + \varepsilon_{ij}$ for subject i at visit j.

If β_3 is significantly negative ($p < .05$), this would indicate that the mechanism variable decreased more in SMT than in MT (Fitzmaurice, Laird, & Ware, 2011). In case of a significant interaction, we will test simple slopes of Time for each Treatment Condition separately AND by testing post treatment differences between MT and SMT controlling for pre-treatment values.

Candidate covariance structures will be assessed using the data's correlation structure and Akaike's Information Criterion (AIC). Random coefficients (e.g. random intercept and/or random slope) will be included in the model if they significantly improve the model fit as determined by the likelihood ratio test. Standardized residuals and Cook's distance will be used to assess the influence of outliers and individual observations. Residual plots will be used to check the multivariate normal distribution assumption. The pattern of missing data will be examined to determine its missing mechanism and the amount. If data are missing not at random (MNAR), data imputations may be used. If other deviations from the model assumptions are detected, appropriate measures will be taken to prevent inferential bias, e.g. data transformations and use of bootstrap techniques to compute standard errors.

Potential covariates (site, age, and any baseline variables found to be significantly different ($p < .20$) between treatment groups) will be considered for model inclusion using a model selection method called least absolute shrinkage and selection operator (LASSO) (Tibshirani, 2011). This method identifies groups of covariates to form a parsimonious model; it avoids problems in stepwise procedures such as collinearity, bias, and variance deflation (Flom & Cassell, 2007); the method has recently been extended to mixed effects models (Bondell, Krishna, & Ghosh, 2010; Fan & Li, 2012; Fernandez, 2007).

Aim 2: To determine whether MT will produce greater improvements in mindfulness-related factors than SMT, and whether SMT will produce greater improvements in spinal stiffness than MT.

The primary analyses will employ the two-sample t-test to compare mean change in each specific mechanism to compare mean change in outcome from pre to post treatment between the two treatment arms. An overall, 2-sided, significance level of 0.05 will be used. Linear mixed models will be used as a supplemental analysis, allowing us to utilize all data collected, account for within subject variation, and model changes over time. The fixed effect part of the model will be

$Mechanism_{ij} = \beta_0 + \beta_1 Time_{ij} + \beta_2 Tx_i + \beta_3 (Tx_i * Time_{ij}) + \varepsilon_{ij}$ for subject i at visit j .

If β_3 is significantly negative ($p < .05$), this would indicate that the mechanism variable decreased more in SMT than in MT (Fitzmaurice, Laird, & Ware, 2011). In case of a significant interaction, we will test simple slopes of Time for each Treatment Condition separately AND by testing post treatment differences between MT and SMT controlling for pre-treatment values. As in Aim 1, we will follow this analysis with generalized linear mixed effects modeling (GLMM) with subject-specific intercepts and subject-specific slopes.

Candidate covariance structures will be assessed using the data's correlation structure and Akaike's Information Criterion (AIC). Random coefficients (e.g. random intercept and/or random slope) will be included in the model if they significantly improve the model fit as determined by the likelihood ratio test. Standardized residuals and Cook's distance will be used to assess the influence of outliers and individual observations. Residual plots will be used to check the multivariate normal distribution assumption. The pattern of missing data will be examined to determine its

missing mechanism and the amount. If data are missing not at random (MNAR), data imputations may be used. If other deviations from the model assumptions are detected, appropriate measures will be taken to prevent inferential bias, e.g. data transformations and use of bootstrap techniques to compute standard errors.

Potential covariates (site, age, and any baseline variables found to be significantly different ($p < .20$) between treatment groups) will be considered for model inclusion using a model selection method called least absolute shrinkage and selection operator (LASSO) (Tibshirani, 2011). This method identifies groups of covariates to form a parsimonious model; it avoids problems in stepwise procedures such as collinearity, bias, and variance deflation (Flom & Cassell, 2007); the method has recently been extended to mixed effects models (Bondell, Krishna, & Ghosh, 2010; Fan & Li, 2012; Fernandez, 2007).

Aim 3: To test the relative predictive validity of non-specific and specific mechanisms.

To test to what degree changes in non-specific and specific mechanisms predict changes in pain, mood and function, and whether these relationships depend on the treatment received, we will first test Mechanism x Treatment interactions to determine whether changes in any of the candidate mechanisms predict outcomes to a greater degree in one treatment over the other. Linear mixed effects regression models will be conducted to test, for example, a non-specific mechanism change score x Treatment interaction for each outcome change. If significant differences are observed, then the interaction effects will be interpreted to provide the unique effect of mechanism change for each treatment group.

In the absence of interactions, we will use linear mixed effects regression models to test the degree to which changes in non-specific and specific mechanisms account for unique and shared variance in pre-post outcome changes. More specifically, 0-order correlations among mechanism and outcome pre-post change scores will reveal “candidate” mechanisms (i.e., those with significant associations with pre-post outcome changes). We will use a series of hierarchical regressions to examine the degree to which ostensibly different mechanisms account for shared or unique variance in outcome changes. Such analyses will allow us to identify common areas of mechanism overlap (e.g., changes in self-efficacy and pain catastrophizing accounting for much shared variance in pain changes), and mechanism uniqueness (e.g., changes in spinal stiffness accounting for significant unique variance in pain changes even with other mechanism changes controlled).

Aim 4: Address competing causation pathways.

First, we will use an approach and techniques that we have used in previous publications [eg, [name], J.W., Nielson, W.R., Jensen, M.P., Heapy, A., Czlapinski, R., & Kerns, R.D. (2015). Specific and general therapeutic mechanisms in cognitive-behavioral treatment of chronic pain. *Journal of Consulting and Clinical Psychology*. 83, 1-11. PMID: 24979313]. Namely, we will test lagged and cross-

lagged effects using pre- to mid-treatment and mid- to post-treatment epochs. Given that endogenous opioid functioning will be assessed only at pre-and post-treatment, and given that the working alliance and subject expectations for benefit will be assessed only at 3- and 6-weeks, this approach will allow to examine comparable effects across all our specific and non-specific mechanisms. Residual change scores for all mechanism and outcome variables will be computed by regressing mid-treatment on pre-treatment values (i.e., a pre-mid residual change score), and regressing post-treatment on mid-treatment values (i.e., mid-post residual change score). For lagged relationships, regressions will be performed to identify the unique effect of pre-mid mechanism changes on mid-post outcome changes. This will require statistically controlling for the path from pre-mid mechanism change to mid-post mechanism change and pre-mid outcome change to mid-post outcome change. See Figure 1 and 2 below. The red line is the target lagged effect. The two blue lines are the paths to be controlled.

Figure 1

[figure not shown]
[figure not shown]

Figure 2

For cross-lagged effects, the procedure will be inverted. Namely, we will test whether pre-mid changes in outcomes predict mid-post changes in mechanisms. Significant lagged effects paired with non-significant cross-lagged effects will add support to the notion that early-treatment changes in putative mechanisms influenced later-treatment changes in outcomes. In general, we expect that pre-mid changes in mindfulness and spinal stiffness will predict mid-post changes in pain interference (and other outcomes), but the inverse will not be the case.

Second, we will take a more fine-grained HLM approach using the weekly data. We will test whether: a) previous week levels of specific (e.g., mindfulness, spinal stiffness) and nonspecific mechanisms (e.g. self-efficacy) predict previous week to next week changes in outcomes; b) these relationships depend on time in treatment (i.e. quadratic trends could emerge indicating that early- vs late-treatment effects are distinct); c) whether the inverse relationships (i.e. outcomes predicting mechanisms) are also significant; d) whether patterns of lagged effects are different between MT and SMT. In general, we expect that previous week levels in mechanisms will predict previous week to current week changes in outcomes, and that the strength of these relationships will be strongest from Week 3 to Week 6 (when specific mechanisms have improved sufficiently to best affect improvements in outcomes).

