work showed small differences lacking clinical meaningfulness when comparing SMT provided 1, 2, or 3 times per week. (88) Furthermore, our visit pattern is consistent with professional guidelines (89,90). Thus, we believe our design is optimal in matching time required for MT sessions and also meeting effective SMT practice patterns. We will administer 2 SMT techniques each session, both of which have demonstrated effectiveness and are common for conservative management of individuals with CLBP. (37,38,91) See Appendix for description and illustrations. We will use scripted interactions between the physical therapist (PT) providing the SMT and subjects to stimulate therapist/subject relationships more consistent with the relationships that will develop in MT. Each SMT session will be organized as follows: 1) Participants will lie on the SMT table for 20 mins, while the PT sits approximately 6 ft away. As part of the script, the PT will review with subjects the inclusion/exclusion criteria ostensibly to ensure that nothing has changed. 2) The PT will perform the 2 SMT techniques during the next 20 mins. 3) Subjects will lie on the SMT table for the remaining 20 mins, while the PT sits approximately 6 feet away. As part of the script, the PT will ask subjects to perform a posterior pelvic tilt exercise. Subjects attempting to enter into discussion of issues beyond the scripted plan will be told, “I’m sorry but because this is a research study I am not allowed to discuss this with you.”

Each individual participant will be in the study for approximately 38 weeks. This includes a baseline assessment, 2 pre-treatment laboratory assessments, 8 therapy sessions, 2 post-treatment assessments, and 3- and 6-month follow-up visits.

Therapist Training, Adherence, Participant Engagement

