consistent with our past work 69-71). As in our past studies, naloxone in 20 ml normal saline will be infused over a 10-minute period through an intravenous cannula placed in the non-dominant arm. At this dosage, naloxone provides effective blockade of all three major opioid receptor subtypes (79). Naloxone is FDA approved, and appears to have no clinical effects in non-opiate dependent individuals. Thus, participants using opioid analgesics on a daily basis or within 3 days of each laboratory session (confirmed via urine drug screen) and/or experiences withdrawal symptoms with the initial naloxone administration, will be excluded. It has been used safely at similar dosages in previous studies, including our studies in CLBP samples (68-72). Peak naloxone activity will be achieved approximately 10 minutes following completion of the infusion. A second dose of naloxone (0.055 mg/kg with a maximum dose of 4mg; 4mg for a 160 lb. individual) will be infused following the thermal and ischemic tasks (before CPM procedures). This dose will be used to maintain adequate opioid blockade across the duration of pain-induction procedures.

The QST protocol will use 2 laboratory pain tasks for evaluation of evoked pain responsiveness. An ischemic pain task will be used based on procedures described by Maurset et al. (80), similar to our past opioid blockade studies (68,72). Subjects will first engage in 2 mins of dominant forearm muscle exercise using a hand dynamometer at 50% of his or her maximal grip strength (as determined prior to beginning laboratory procedures), and then will be asked to raise the dominant forearm over their head for 15 secs. A blood pressure cuff will then be inflated on the participant's dominant biceps to 200 mmHg pressure, and the cuff will remain inflated until tolerance is reached, up to a maximum of 8 mins. As in our previous work (68,72), at 30-sec intervals throughout the ischemic task, participants will be asked to rate their current acute pain using a 0-100 verbal numeric rating scale (0 = "no pain" and 100 = "worst possible pain"). Pain threshold will be defined as time elapsed from task onset to when the sensation is first described as "painful." Pain tolerance will be defined as time elapsed between onset of the pain task and patients' expressed desire to terminate the task (8 min max). At tolerance, subjects will be asked to rate the overall ischemic task pain intensity using the McGill Pain Questionnaire (MPQ; see below).

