A heat pain task using a Medoc TSAII NeuroSensory Analyzer (Medoc US., Minneapolis, MN) will then follow. This equipment will be used to assess heat pain threshold and tolerance using an ascending method of limits protocol as used in our prior work (68,71,72). The equipment to be used has a hardware temperature cutoff of 51°C in order to prevent tissue injury. Four trials each will be conducted for heat pain threshold and tolerance, with each trial conducted sequentially at 1 of 4 different non-overlapping sites on the non-dominant ventral forearm. An interval of 30 secs between successive stimuli will be employed. For threshold trials, the probe will start at an adaptation temp of 32°C, with the temp increasing at a ramp rate of 0.5°C/sec until the subject indicates that the stimulus has begun to feel "painful." For tolerance trials, the probe will start at an adaptation temperature of 40°C, with the temperature increasing at a ramp rate of 0.5°C/sec until the subject indicates maximum tolerance has been reached. Means of the 4 thermal pain threshold and tolerance trials will be derived for use in analyses. Immediately upon completion of the final heat pain tolerance trial, subjects will be asked to rate the overall pain experienced during this

trial using the MPQ. EO function will be operationalized as in our past work as changes in evoked pain responses between the placebo and naloxone conditions (68,71,72), with blockade effects on the visual analog scale (VAS) pain intensity measure of the MPQ considered primary.

Conditioned Pain Modulation (CPM)

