Assessment of spinal stiffness

The VerteTrack device (VibeDx Diagnostic Corp) will be used to measure the lumbar posterior to anterior spinal stiffness, with L3 values considered primary per validation studies (40,103). The VerteTrack device has not been approved by the FDA. The device consists of a solid aluminum gantry (Width 108cm × Height 109cm × Length 151cm) on lockable casters that can be positioned over a participant lying in the prone position on a standard padded-plinth. Each assessment takes approximately 15 mins.

Two types of spinal stiffness values will be calculated from the force displacement data of each indentation: global stiffness and terminal stiffness. Global stiffness will be calculated from the slope of force displacement curve between 5 Newtons (N) and 60 N, representing the stiffness of underlying tissues throughout the indentation (39). Terminal stiffness is a ratio between the maximal applied force (60 N) and maximal resultant displacement, representing stiffness at the end of indentation (39). Spinal stiffness will be measured 3 times at each assessment. Averaging 3 measurements, within- and between-day reliability point estimates of both global and terminal stiffness were 0.99 and 0.98, respectively (40).

Randomization

Study subjects will be randomized to receive either MT or SMT. The order of drug administration for each laboratory session will also be randomized and counterbalanced (placebo vs. naloxone), and double-blinded. These randomizations will occur prior to the baseline screening visit (Visit 1). All randomization will be carried out using the Proc Plan procedure in SAS version 9.2 (SAS Institute, Cary, NC). This SAS procedure will be used to generate a randomization schedule for each sequential study slot (MT vs. SMT and the order of naloxone/placebo administration in each set of lab visits). Study subjects will be assigned to these previously randomized study slots in the order that they are enrolled, and the previously determined randomization status associated with each slot will determine the study condition each subject is in and the order of drug administration.

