9.3 Definition of Populations

The ITT (intent to treat) sample will be all subjects who complete baseline measures. The “per protocol” sample (i.e., “treatment completers”) will be those subjects who complete at least 6 of the 8 treatment sessions.

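### The primary Aim 1 test is labelled ITT but, without optional imputation, is an unadjusted t-test on people with all four lab sessions; the model using all data is only supplemental and is not compared with the equivalence limits

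*Protocol*

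**What the plan says.** - Analysis set: "Primary analyses will be conducted on an ITT basis" (Protocol 9.6), and "The ITT (intent to treat) sample will be all subjects who complete baseline measures" (9.3). Neither statement requires post-treatment data.
- Primary test: "The primary analyses will employ the two-sample t-test to compare mean change in each nonspecific mechanism" (9.6, Aim 1), applied to change from before to after treatment. Section 9.5.1 names change in EO function as the primary mechanism outcome.
- The score: "EO function will be operationalized as in our past work as changes in evoked pain responses between the placebo and naloxone conditions" (6.2.2). The visit plan has "2 pre-treatment laboratory assessments, 8 therapy sessions, 2 post-treatment assessments" (5.1), and each pair of labs supplies one placebo and one naloxone session.
- All-data model: 9.6 makes the linear mixed model supplemental. Its treatment-by-time coefficient is interpreted when significant at p<.05. The equivalence limits of -3 and 3 appear only in 9.2.
- Missing data: 9.6 says the pattern will be examined and permits, but does not require, imputation if data are missing not at random.
- Losses the protocol foresees: 6.2.2 excludes "participants using opioid analgesics on a daily basis or within 3 days of each laboratory session", and 6.2.4 repeats the urine opioid test at the post-treatment labs. Section 8 promises effort to obtain follow-up assessments from those who stop.

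**The concern.** The label and the test describe different sets of people. A two-sample t-test on change can use a participant only if the change exists, and one EO change score takes four lab sessions. Someone who completes baseline and treatment but misses one post-treatment lab, or is excluded at it for recent opioid use, remains in the ITT set and drops out of the primary test.

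The protocol's hypothesis for EO function is near-equivalence, so this matters in both directions. If the arm difference among those lost is not the same as among those observed, equivalence may be declared too often or missed. Loss through opioid use could plausibly be related to pain response. The effort promised in section 8 limits such loss but does not say how people still lacking EO data are analysed.

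The test is also unadjusted. Pre-treatment EO is measured in everyone who reaches the first pair of labs, but it enters only the follow-up to a significant interaction, or possibly the covariate selection in 9.6. The interval may therefore be wider than the collected data require.

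**Working it through.** **1. The plan's own figure.** Inputs from 9.2: 120 per arm, SD 7.5, true difference 0, two one-sided t-tests at 0.05 each. The standard error is 7.5 × √(2/120) = 0.968. Integrating over the sample variance (df 238) gives power 0.851, 0.950 and 0.987 for limits of 3.0, 3.5 and 4.0. These match the table. The inflation also holds: 240/0.84 = 286.

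**2. Who the t-test can use.** EO at one time point = response under placebo compared with response under naloxone = 2 sessions. Change = post minus pre = 4 sessions. The number who will lack one is not stated. The 16% in the Précis refers to completing follow-up, not to having all four labs.

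**3. Reading the supplemental model.** At 120 per arm the interaction is non-significant for observed differences up to 1.97 × 0.968 = 1.91. Equivalence within ±3 requires an observed difference below 3 − 1.651 × 0.968 = 1.40. At a true difference of 3.0 the interaction is non-significant about 13% of the time. The model as specified therefore cannot support an equivalence statement.

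**4. Selective loss (illustration only).** Let m be the fraction lacking EO change, equal in both arms, and d the arm difference in the missing minus that in the observed. With a true ITT difference of 3.0, the observed difference is 3.0 − m × d, with 143 × (1 − m) per arm. Chance of declaring equivalence (5% when d = 0):

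| m | d = +2 / +4 / +6 | d = −2 / −4 / −6 |
|---|---|---|
| 5% | .062 / .077 / .094 | .040 / .031 / .024 |
| 10% | .076 / .112 / .158 | .032 / .019 / .011 |
| 16% | .094 / .162 / .256 | .024 / .011 / .004 |

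At a true difference of 0 with m = 16%, power is .852, .830, .767 and .669 for d of size 0, 2, 4 and 6, either sign. No section supports a particular m or d. The most extreme cell implies an arm difference among the missing of 3.0 − 0.96 + 6 = 8.04, which is more than one SD.

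**5. Baseline adjustment.** Assume equal pre and post variances and a pre-post correlation r; df 237.

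- If 7.5 is the SD of change, adjustment multiplies the variance by (1 + r)/2. For r = 0.2, 0.5 and 0.8 the SD becomes 5.81, 6.50 and 7.12, and power becomes 0.98, 0.95 and 0.89, against 0.85 unadjusted.
- If 7.5 is the SD at one time point, the t-test SD is 7.5 × √(2(1 − r)) = 9.49, 7.50 and 4.74, with power 0.575, 0.851 and 0.999. The adjusted SD is 7.5 × √(1 − r²) = 7.35, 6.50 and 4.50, with power 0.869, 0.945 and 1.000.

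Section 9.2 does not say which SD is meant. Adjustment helps in either case.

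**6. Recovering partial data.** Take 120 complete and 23 pre-only participants per arm, and the unconstrained likelihood model of 9.6. The variance of the arm contrast in change, relative to the complete-case t-test, is [(1 + r) + (1 − r) × 120/143]/2 = 0.94, 0.96 and 0.98. If 7.5 is the SD of change, power moves from 0.85 to 0.88, 0.87 and 0.86. The gain is small.

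**The case against.** The strongest reply is that missing-data rules, covariate lists and sensitivity analyses usually belong in the SAP, which is not to hand. Section 9.6 does allow imputation, and 10.2 makes the principal investigators responsible for handling missing data and correcting bias. This stands against any complaint about absent detail. It does not answer the mismatch, because the protocol itself fixes the set, the primary test and the model's lower rank.

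Other parts of the reply stand:

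- A reader might infer that everyone lost at the pre-treatment labs is an ITT member whom the test drops. The documents do not settle this. Section 6.2.2 calls the opioid testing at Visits 2 and 3 a baseline assessment, while the table in 6.1 puts those labs in columns separate from Baseline. The case rests mainly on post-treatment loss.
- A reader might infer that the plan takes a non-significant interaction as proof of equivalence. Section 9.6 never says so. Nor does it restate the 9.2 limits for the t-test; it refers only to a noninferiority framework.
- A reader might take the 26% in the table as an expected error rate. It requires a true difference exactly at the limit, 16% loss and a very large arm difference among the missing. With balanced 16% loss and no difference among completers, the missing would have to differ by 3/0.16 = 18.75 points, or 2.5 SD, to bring the overall difference to 3.
- The reduced numbers are already planned for: 9.2 computes power on 240, not 286.
- Replacing the test recovers few people. The two post-treatment labs are due within 2 weeks of each other (6.2.6), so many of those lost may have neither.

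**Conclusion.** The point holds as a should-fix matter, with medium confidence. As written, the primary Aim 1 result would be reported as ITT while resting on people with complete EO data, unless the optional imputation is used. The trigger for imputation is not workable, because observed data cannot establish that data are missing not at random.

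The t-test is valid with complete data, and loss unrelated to the arm difference causes no bias. Otherwise the bias has unknown size and direction; the 5-16% loss and 2-6 point shifts are illustrations. The documents do not support a claim that the equivalence conclusion is wrong or that its error rate is materially inflated.

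The firmer gain is precision: power of about 0.89-0.98 instead of 0.85, if 7.5 is the SD of change, variances are equal and the pre-post correlation is 0.8-0.2. Using partial data adds little to that.

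**What to change.** - Make the primary Aim 1 analysis a mixed model with a common baseline mean across arms, which adjusts for pre-treatment EO. Fit it either to the session-level MPQ VAS scores (drug, time, arm and their interactions) or to the pre and post EO scores. Include site and drug order; no particular gain is claimed for drug order.
- Include everyone with any lab session that the chosen form can use, under a stated missing-at-random assumption. Compare the arm contrast in pre-post change with the section 9.2 limits.
- Replace the missing-not-at-random trigger with a prespecified delta-shift sensitivity analysis in both directions. Outcome-related loss is addressed only here, because the model cannot recover EO change for people with no post-treatment lab.
- State whether the pre-treatment labs count as baseline measures for the ITT set, and report how many ITT members lack each lab session.
- Keep the t-test as a supportive analysis, labelled complete-outcome.

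The cost is some programming, an explicit missing-at-random assumption and a protocol amendment. No further participants or measurements are needed. The revision history lists version 20, dated June 2024, so the amendment would be late and should be justified and dated before any analysis by arm.
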